9. STUDY ENDPOINTS

9.1. The primary outcomes:

- **Efficacy endpoint**

- 1- Change in WHO Ordinal Scale for clinical improvement (baseline to end of study will be measured on days 1,7,14 and 28).

The World Health Organization (WHO-WHO) has proposed the “Ordinal Scale of Clinical Evaluation of the World Health Organization” presented below as a means of generating a numerical value to assess the health status of the participant to allow comparisons to be made in clinical studies. The scale is shown in the table below and will be used to assess a secondary effectiveness target in this study.

Patient State	Descriptor	Score
Uninfected	Uninfected; no clinical evidence and viral RNA detected	0
Ambulatory	Symptomatic; independent	1
	Symptomatic; assistance needed	2
Hospitalized: Moderate diseases	Hospitalized, no oxygen therapy	3
	Hospitalized; oxygen by mask or nasal prongs	4

	MGC Pharma Clinical Study Protocol	Protocol No.: MGC-009
		Version 02, 05 Sep 2021
		Page 34 of 76
A Phase IIb, double blind, placebo-controlled clinical study designed to evaluate the effect of CimetrA in patients diagnosed with COVID-19		CONFIDENTIAL

Hospitalized: Severe diseases	Hospitalized; oxygen by NIV or high flow	5
	Hospitalized; mechanical ventilation	6
	Mechanical ventilation and vasopressors, dialysis or ECMO	7
Dead	Dead	8

2- Change in COVID-19-Related Symptoms score (measured on days 1,7, 14, 28)

• **Safety Endpoints**

Safety will be assessed through collection and analysis of adverse events, blood and urine laboratory assessments and vital signs.

9.2. **The secondary outcomes:**

- Number of participants with depending on oxygen supplementation through day 28 since onset of symptoms
- Change in inflammatory marker levels - IL-6, IL-1 β , IL-12, TNF α , IFN- γ , CRP, NLR (Neutrophil / Lymphocyte ratio) (days 1, 2, 4, 7) compared to baseline
- Pharmacokinetic profile of the study drug on day 1 through 24 Hrs.
- Incidence and duration of mechanical ventilation
- Incidence of Intensive Care Unit (ICU) stay during COVID-19 complication
- Percentage of participants with definite or probable drug related adverse events
- Long term adverse events of COVID-19 on Day 28
- The Impact covid_19 on quality of life of patients on Days 1, 14 and 28

9.3. **The exploratory outcomes:**

- Course of change in D Dimer levels compared to baseline

	MGC Pharma Clinical Study Protocol	Protocol No.: MGC-009
		Version 02, 05 Sep 2021
		Page 35 of 76

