A Phase IIb, double blind, placebo-controlled clinical study designed to evaluate the effect of CimetrA in patients diagnosed with COVID-19		CONFIDENTIAL

- Occurrence of secondary infections

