10.2. Trial entry and enrollment: Medication schedule

Study drug will be administrated twice a day during days 1 and 2. Patients will be monitored for adverse events.

10.2.1. Clinical and laboratory follow up:

Subjects will be followed through regularly scheduled visits that will include: vital signs, physical examination, ongoing medical history review, and laboratory tests as described in Table 5.

Safety will be assessed by monitoring the subjects for AEs. The subjects will be instructed as to what is an AE and will be requested to fill out a diary detailing any AEs that may occur during the time period between visits.

Evaluation of the effect of oral administration of the study drug will be assessed by determining the clinical and laboratory tests as summarized below.

	MGC Pharma Clinical Study Protocol	Protocol No.: MGC-009
		Version 02, 05 Sep 2021
		Page 38 of 76
A Phase IIb, double blind, placebo-controlled clinical study designed to evaluate the effect of CimetrA in patients diagnosed with COVID-19		CONFIDENTIAL

Table 5: Schedule of events

Day	1	2	3-6	7	8-13	14	Day 21(phone visit)	Day 28 Clinic visit
Confirmed SARS-CoV-2 infection	X					X		X
Treatment administration (twice a day)	X	X						
Inclusion/Exclusion criteria evaluation	X							
Informed Consent	X							
Medical History	X							
Concomitant Medications	X	X	X	X	X	X	X	X
AE Assessment		X	X	X	X	X	X	X
Randomization	X							
Physical Examination	X	X	X	X	X	X		X
Vital Signs	X	X	X	X	X	X		X
Hematology blood test (local)	X	X	X**	X	X**	X		X
Biochemistry blood test (local)	X	X	X**	X	X**	X		X
WHO Ordinal Score	X			X		X	X	X
COVID-19-Related Symptoms assessment	X			X		X	X	X
PK test*	X							
Blood test for inflammatory markers (IL-6, IL-1 β , IL-12, TNF α , IFN- γ) (local)	X	X	X	X		X		X

	MGC Pharma Clinical Study Protocol	Protocol No.: MGC-009
		Version 02, 05 Sep 2021
		Page 39 of 76
A Phase IIb, double blind, placebo-controlled clinical study designed to evaluate the effect of Cimetra in patients diagnosed with COVID-19		CONFIDENTIAL

D-Dimer test (local)	X	X		X		X		X
VAS scale	X	X	X	X	X	X	X	X
Urine pregnancy test for women of childbearing potential	X							X
ECG	X							x
COVID-19–Impact on Quality of Life Questionnaire	X			X	X	X	X	X
POST- COVID-19 Functional Status Scale								X

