17. STATISTICAL METHODS AND DETERMINATION OF SAMPLE SIZE

A prospective, randomized (1:1:1), double-blind, multi-center, placebo-controlled clinical study.

Statistical Hypothesis

The hypothesis of this study is that treating with CimetrA and CimetrA2 will be more effective, while maintaining a favorable safety profile. This will be demonstrated by a significant difference between the two active and the control groups.

	MGC Pharma Clinical Study Protocol	Protocol No.: MGC-009
		Version 02, 05 Sep 2021
		Page 60 of 76
A Phase IIb, double blind, placebo-controlled clinical study designed to evaluate the effect of Cimetra in patients diagnosed with COVID-19		CONFIDENTIAL

In this study, we will test the following hypothesis:

- H0: $\Delta_1 = \Delta_2 = \Delta_3$
- H1: at least one is different.

Where Delta is the difference between baseline and end of study in WHO Ordinal Scale for clinical trial.

If the null hypothesis is rejected in favor of the alternative hypothesis the study will be deemed successful.

Safety will be assessed by adverse events, blood and urine laboratory assessments and vital signs.

Planned Sample Size

For this phase IIb, 3-armed clinical trial, we use the ANOVA test to estimate the expected improvement in the primary outcome; the WHO ordinal scale for clinical improvement.

We expect medium effect ($f=0.20$) for the differences in Delta between the 3 groups, and standard deviation of 1.5, based on the ordinal scale (0-8). This power analysis is for a one-way fixed effects analysis of variance with 3 levels. The study will include 80 patients per group for a total of 240 patients.

The criterion for significance (α) has been set at 0.05 with Power of at least 80%.

The analysis of variance is two-tailed Main effects.

For immunogenicity assessment, larger sample size will reduce mean variability in the observed outcomes and will increase the opportunity to detect real changes.

For 80 participants per group we ensure the desired precision for phase 3 trial to assess safety and effectiveness. Total sample 240 patients.

Computer Software

	MGC Pharma Clinical Study Protocol	Protocol No.: MGC-009
		Version 02, 05 Sep 2021
		Page 61 of 76
A Phase IIb, double blind, placebo-controlled clinical study designed to evaluate the effect of CimetrA in patients diagnosed with COVID-19		CONFIDENTIAL

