A Phase IIb, double blind, placebo-controlled clinical study designed to evaluate the effect of CimetrA in patients diagnosed with COVID-19		CONFIDENTIAL

The 3 groups will be compared with the ANOVA test or Kruskal Wallis non-parametric test, following by post-hoc analysis for pairs differences.

Additional Efficacy Parameters of Interest

A count and percentage of participants responding to each of the exploratory efficacy endpoints will be presented. The groups will be compared with a chi-squared test or a Fisher’s exact test.

Safety Analysis

The primary safety variable, the cumulative incidence (and 95% CI) of device related adverse events (AEs) throughout the study, will be presented in tabular format and will include incidence tables by severity.

Serious adverse events, device-related SAEs, adverse events (by type and overall), device-related AE, adverse device reactions and device malfunction rates will be compared between the study arms with a Fisher’s exact test.

Serious adverse events will be listed and discussed individually.

PK test

Actual times of dosing and blood collection at various time points will be recorded in source documents as well as CRF’s. Objectives of PK sampling are to measure values of CimetrA active ingredients in plasma at different time point after first administration of study medications and at different time point after multiple administrations during steady state.

PK samples will be processed and frozen on site. Labels have been prepared for the site again containing patient No., visit No., type of test (PK) and time point. Upon completion of the study, samples will be sent to selected analytical laboratory with dedicated courier service. The PK parameters will be obtained from plasma concentration data for curcumin and boswellia.

	MGC Pharma Clinical Study Protocol	Protocol No.: MGC-009
		Version 02, 05 Sep 2021
		Page 65 of 76
A Phase IIb, double blind, placebo-controlled clinical study designed to evaluate the effect of Cimetra in patients diagnosed with COVID-19		CONFIDENTIAL

Analyses of PK data will be based on the PK Set, which will include all subjects who received at least one treatment and for whom concentration data is available.

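### D-dimer is defined as a course of change from baseline, but section 17 analyses it as a count of responders by chi-squared or Fisher's exact test

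*Protocol*

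**What the plan says.** Section 9.3, and the synopsis in the same words, lists two exploratory outcomes. The first is "Course of change in D Dimer levels compared to baseline". The second is "Occurrence of secondary infections".

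Table 5 and the day-by-day lists in section 10.2.1 schedule a D-dimer test at the local laboratory on days 1, 2, 7, 14 and 28. That is one baseline value and up to four later ones per patient.

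Section 17, under Additional Efficacy Parameters of Interest, states the analysis: "A count and percentage of participants responding to each of the exploratory efficacy endpoints will be presented". It continues: "The groups will be compared with a chi-squared test or a Fisher’s exact test".

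The paragraph just before it, under Secondary Efficacy Analysis, uses methods for continuous data: "The 3 groups will be compared with the ANOVA test or Kruskal Wallis non-parametric test". D-dimer is not among the secondary outcomes in section 9.2, so that sentence does not reach it.

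**The concern.** The outcome and its analysis are of different kinds. Section 9.3 asks how a laboratory value moves over time relative to its starting point. Section 17 answers with the proportion of patients who count as responders. The methods do not describe the outcome, and the protocol assigns D-dimer no other analysis.

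At stake is the use made of data already being collected. The cytokines, CRP and the neutrophil/lymphocyte ratio are drawn from the same patients on overlapping days and are compared with methods suited to continuous values, because they are secondary outcomes. D-dimer, a similar serial marker, would be cut into two classes. The result would depend on where the cut falls, and the pattern over days 2 to 28 would be lost or shown only crudely.

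**Working it through.** **Does the rule cover D-dimer?** Section 17 applies it to each exploratory efficacy endpoint. The protocol's only exploratory list is section 9.3, repeated in the synopsis, and it has two entries. Section 9.3 speaks of outcomes and section 17 of efficacy endpoints, but there is no other list to which section 17 could refer. D-dimer is therefore covered.

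**Does the rule fit each entry?**

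| Exploratory outcome | Type | Count with chi-squared or Fisher |
|---|---|---|
| Secondary infections | Yes/no event | Fits |
| Course of change in D-dimer | Continuous, one baseline and four later days | Gives a proportion, not a course of change |

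**Does another sentence rescue it?** The ANOVA/Kruskal-Wallis sentence is confined to secondary outcomes. The instruction to compare arms according to data type concerns demographic and baseline characteristics only. No change-from-baseline or repeated-measures analysis is assigned to D-dimer.

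**What does dichotomising cost?** The protocol gives no D-dimer figure to reproduce, so what follows is illustration.

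*General result.* For a normal variable, the efficiency of a median split relative to comparing means is 2/pi = 2/3.1416 = 0.64.

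*Illustration in a trial of this size.* Assume a normal endpoint, 80 per arm, alpha 0.05 and effect f = 0.20. The f value is borrowed from the WHO-scale sample size in section 17; the protocol does not claim it for D-dimer.

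- Analysed as continuous (one-way ANOVA, three arms): noncentrality = N × f² = 240 × 0.04 = 9.6, which gives power of 79.3%. This is within one point of the 80% that section 17 states for the WHO scale.
- Analysed as responders (3 × 2 chi-squared, 2 df): noncentrality = n × Σ(pᵢ − p̄)² / [p̄(1 − p̄)], where pᵢ is the proportion beyond the cut-off in arm i.
- Two patterns give f = 0.20. In one, both active arms differ from control by 0.20 × 3/√2 = 0.424 SD. In the other, the shift is graded up to 0.20 × √6 = 0.490 SD, with the middle arm halfway.

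| Cut-off (SD from control mean) | Power, both active arms equal | Power, graded |
|---|---|---|
| 0 | 58.8% | 57.3% |
| 0.5 | 56.2% | 57.3% |
| 1.0 | 45.7% | 49.1% |
| 1.5 | 30.8% | 35.1% |

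For the first row with equal active arms, the proportions are 0.500, 0.664 and 0.664, the noncentrality is about 6.0, and 6.0/9.6 = 0.63, in line with 2/pi. Power thus falls from about 79% to between 57% and 59% at a cut on the control mean, and to between 31% and 35% at 1.5 SD. The sign of the shift does not matter, so the same holds for a fall in D-dimer.

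**Would a cut-off in the analysis plan settle it?** No. The protocol has already fixed the summary and the test. An analysis plan that adds a cut-off still reports a response rate, and one that analyses change from baseline departs from the protocol.

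**The case against.** The strongest reply is that a responder definition for an exploratory laboratory marker is normal content for a statistical analysis plan, and that plan is not at hand. That stands: the missing cut-off and day are not counted here. The mismatch remains once they are supplied.

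A second reply is that the percentage of patients with a defined fall from baseline, shown by scheduled day, does describe change, though coarsely, and that section 17 does not forbid further descriptive summaries. That also stands. It would be too strong to say that the stated rule can tell the reader nothing about change. The rule is a poor match for the outcome and wastes information.

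Three stronger readings are tempting, and the protocol supports none of them:

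- *That the threshold would be picked after the data are seen.* Nothing says so; it could be fixed before unblinding.
- *That local laboratories in four countries make a common absolute cut-off invalid.* The protocol proposes no absolute cut-off. The outcome is relative to baseline, so a response could be defined against the patient's own value.
- *That the case for Boswellia rests on D-dimer.* Section 4.2 does mention coagulation, but it also cites effects on endothelial adhesion molecules and antioxidant, anti-inflammatory and immunomodulatory effects. TNF-alpha and other inflammatory markers are secondary outcomes with a continuous-data test.

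Finally, the protocol claims no power for D-dimer, so no stated figure is wrong.

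**Conclusion.** The point holds as a mismatch between sections 9.3 and 17, confined to D-dimer. The stated rule would replace a course of change with a response rate. The loss is about one third of the information at best (a median split keeps about 64%) and more at other cut-offs. This size assumes an approximately normal variable, perhaps after a log transformation, and the power figures also assume an effect borrowed from another endpoint.

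The consequence is minor. The outcome is exploratory, and the primary analysis, alpha, sample size and success criterion are untouched. It is worth correcting because a better analysis uses data already scheduled.

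**What to change.** In section 17:

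1. Restrict the count and percentage, with the chi-squared or Fisher's exact test, to secondary infections.
2. Analyse D-dimer as the log ratio to the day 1 pre-dose value, adjusted for the log day 1 value and for centre, by which the Randomization paragraph stratifies. One repeated-measures model over days 2, 7, 14 and 28 is preferable to four separate comparisons, which would leave open which day counts.
3. State the limit on the data. Section 10 moves discharged patients to phone visits until the day 28 clinic visit, so day 7 and day 14 values may come mainly from patients still in hospital, a group formed after randomisation. Comparisons on those days need caution. Day 28 values may also be missing for patients in quarantine, whose visit is by phone.

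If a response rate is what is wanted, the alternative is to redefine the outcome in section 9.3 and the synopsis as a response with a pre-stated cut-off and day. That removes the contradiction but keeps the loss of information.

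The cost is a few sentences in section 17, with no new samples, visits or patients.

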	MGC Pharma Clinical Study Protocol	Protocol No.: MGC-009
		Version 02, 05 Sep 2021
		Page 16 of 76
A Phase IIb, double blind, placebo-controlled clinical study designed to evaluate the effect of CimetrA in patients diagnosed with COVID-19		CONFIDENTIAL

far, support a central role for immune dysregulation in giving rise to the severe manifestations of COVID-19 [21, 29-31].

Oxidative stress – The damaging effect of this factor has been implicated in the pathogenesis of severe lung injury [32] and specifically proposed play a role in the clinical deterioration in patients with COVID-19 [33].

4. **STUDY PRODUCT**

CimetrA is a Botanical Drug which is comprised of natural active ingredients and formulated in microscopic structures known as micelles. The elements forming the structure of these micelles are in themselves also of exclusively natural origin. The unique formulation is endowed with highly desirable pharmacological features, providing otherwise unattainable high bioavailability to the active ingredients it is designed to deliver.

4.1. **Curcumin**

Curcumin – Curcumin has been noted to possess beneficial effects on human health since antiquity [34]. Over decades of research multiple modes of its action have been studied in vitro and in vivo in laboratories as well as in clinical trials in humans [35]. The resulting data provide ample evidence of clinically significant anti-inflammatory [36], immune-modulatory [37], antioxidant [38], anti-aggregant [39] and antimicrobial [40] activities of curcumin.

Of particular interest are the desirable effects curcumin has demonstrated in models of acute lung injury including down regulation of inflammatory cytokines, decreased infiltration and activation of inflammatory cells and accompanying pulmonary edema, and corresponding improvement of survival [41].

	MGC Pharma Clinical Study Protocol	Protocol No.: MGC-009
		Version 02, 05 Sep 2021
		Page 17 of 76
A Phase IIb, double blind, placebo-controlled clinical study designed to evaluate the effect of CimetrA in patients diagnosed with COVID-19		CONFIDENTIAL

4.2. **Boswellia**

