12.2. Packaging and Labelling of Study Products

CimetrA-1, CimetrA-2 and Placebo is supplied in a bottle containing 5 ml.

The Product is packed in a bottles with a spray pump. It is administered by spraying into the oral cavity.

bottles are closed with a validated spray delivery system , Spray pump on product bottle enables dosing 0.2 ml of CimetrA-1 /0.14 ml of CimetrA-2 in each press and will be packaged and labelled in compliance with the GMP, and EU regulation regarding drugs used in clinical trials.

The lot number and date of manufacture for the clinical lot used in the study will be provided to the clinical site and will be reported in the Clinical Study Report. The documentation supplied by the Sponsor for the study medication (i.e. Certificate of

	MGC Pharma Clinical Study Protocol	Protocol No.: MGC-009
		Version 02, 05 Sep 2021
		Page 51 of 76
A Phase IIb, double blind, placebo-controlled clinical study designed to evaluate the effect of CimetrA in patients diagnosed with COVID-19		CONFIDENTIAL

Analysis for the test product) will make it possible to retrace the composition and pharmaceutical profiles of the test product .

Study Product will be labeled with :

- Product name
- Dose
- Lot number
- Date of manufacture
- Protocol number
- Sponsor's name
- Instructions for use and storage
- "Investigational Use Only" statement

Placebo will be administrated in the same way, and will be identical in its characteristics to the study drug in order to prevent bias.

12.3. **Storage, Dispensing and Return of the Investigational product**

Bottles containing the study product should be stored at room temperature. Records should also be kept by the Investigator or pharmacist as to how much study drug was used by each subject. The study monitors must check during each visit the study drug supplied to ensure expiry date and sufficient amount of study drug. All investigational products must be kept in a locked area with access to the study drug limited to designated study personnel. Only personnel under the supervision of either the Investigator or the local pharmacist are authorized to dispense study drug. During storage at the pharmacy, the temperature will be monitored and recorded by a pharmacist or a temperature log. The Sponsor will be notified for any deviation from the storage conditions.

	MGC Pharma Clinical Study Protocol	Protocol No.: MGC-009
		Version 02, 05 Sep 2021
		Page 52 of 76

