		Version 02, 05 Sep 2021
		Page 56 of 76
A Phase IIb, double blind, placebo-controlled clinical study designed to evaluate the effect of CimetrA in patients diagnosed with COVID-19		CONFIDENTIAL

- likelihood of causality with study product
- outcome of the adverse event

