The overall significance level for this study is 5% using two-tailed tests, except for treatment by center/region interaction that will be tested at a significance level of 10%.

When multiple comparisons between the groups are made, the chance of finding a significant difference in one of the comparisons is greater than the stated significance level, therefore we will use pot-hoc analysis.

Efficacy endpoints:

Time to sustained clinical improvement (as defined earlier).

Safety Endpoints

The safety endpoints of adverse events and tolerability will be assessed by review of all safety parameters, including adverse events.

	MGC Pharma Clinical Study Protocol	Protocol No.: MGC-009
		Version 02, 05 Sep 2021
		Page 63 of 76
A Phase IIb, double blind, placebo-controlled clinical study designed to evaluate the effect of CimetrA in patients diagnosed with COVID-19		CONFIDENTIAL

The incidence of adverse events will be assessed as a function of severity and association to the device. The time of resolution of the adverse events and need for treatment will also be analyzed.

Analysis Sets

The ITT analysis set will serve as the main set for safety assessments.

The primary and secondary performance efficacy assessments will also be performed on the PP and the ITT analysis sets.

Statistical Analysis

Demographic and Baseline

Demographic and baseline condition related characteristics will be tabulated and compared between the study arms by data type. Continuous variables will be summarized by a mean, standard deviation, minimum, median and maximum and categorical variables by a count and percentage.

Primary Efficacy Analysis

The primary efficacy endpoint of the study is the mean change in the WHO Ordinal Scale. It will be evaluated using a General Linear Model ANOVA test.

Subset Analyses

The primary endpoint will also be evaluated stratified by center using a General Linear Model ANOVA test.

A sensitivity analysis of the primary endpoint will be performed to assess the impact of missing data on the study outcome.

Adjustment for other covariates such as demographics or other baseline participant characteristics may be performed by adding these variables into a multivariate linear regression.

Secondary Efficacy Analysis

	MGC Pharma Clinical Study Protocol	Protocol No.: MGC-009
		Version 02, 05 Sep 2021
		Page 64 of 76

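### Section 17 defines the primary safety variable and every related-event comparison on a device that the trial does not have, so they cannot be derived from the causality data collected

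*Protocol*

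**What the plan says.** The safety parts of protocol section 17 use device terms throughout for relatedness.

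- Safety Endpoints: "The incidence of adverse events will be assessed as a function of severity and association to the device".
- Safety Analysis, headline measure: "The primary safety variable, the cumulative incidence (and 95% CI) of device related adverse events (AEs) throughout the study", to be tabulated with a breakdown by severity.
- Safety Analysis, comparisons between arms by Fisher's exact test: "Serious adverse events, device-related SAEs, adverse events (by type and overall), device-related AE, adverse device reactions and device malfunction rates".

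Other sections describe a drug trial.

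- Section 4: "CimetrA is a Botanical Drug which is comprised of natural active ingredients".
- Section 12.2 mentions the spray pump only as part of the packaging: "bottles are closed with a validated spray delivery system".
- Section 14.2 asks the investigator to judge, for each AE, the "likelihood of causality with study product". Section 14.3 speaks of causality between the study drug and the AE.
- Section 9.2 lists as a secondary outcome: "Percentage of participants with definite or probable drug related adverse events".
- Section 9.1 sets the safety endpoint as adverse events, laboratory assessments and vital signs, with no device term.

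**The concern.** The protocol itself fixes the primary safety variable, so this is not a detail left to the statistical analysis plan. An analysis plan that follows section 17 inherits a variable with no source field. One that departs from it contradicts the approved protocol.

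The analyst has to guess what *device* stands for, either the study product or the pump, and also which causality categories count as related. Section 17 answers neither question. Section 9.2 answers the second, but only for a secondary outcome that has no matching analysis in section 17. If these choices are left open until the data are in hand, the headline rate of related events becomes discretionary. The hypothesis in section 17 refers to a favourable safety profile, so the variable that summarises related harm should be unambiguous.

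**Working it through.** **1. Is any study device defined?** No. The arms (section 12.1) are two strengths of a botanical drug and a placebo, all given by oral spray. The only device-like component is the pump (section 12.2). The protocol does not describe it as under investigation, and no pump-specific event or causality question is collected.

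**2. Can each section 17 safety item be derived from what is collected?**

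| Item in section 17 | Causality or data needed | Collected? |
|---|---|---|
| Device-related AEs, cumulative incidence (primary safety variable) | Causality to a device | No; 14.2 records causality to study product |
| AEs by association to the device | Causality to a device | No |
| Device-related SAEs | Causality to a device | No; the 14.5 report has a causality assessment but names no device |
| Device-related AE (comparison between arms) | Causality to a device | No |
| Adverse device reactions | Definition of a device reaction | Not defined |
| Device malfunction rates | Malfunction reports | Not defined |
| All SAEs | None | Yes |
| All AEs, by type and overall | None | Yes |

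So the primary safety variable and four of the six items in the Fisher comparison depend on the undefined device. The two that do not are all SAEs and all AEs.

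**3. Does section 17 analyse the section 9.2 drug-related outcome?** Not by name. Every relatedness-based item in section 17 is a device item.

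**4. Size under the pump reading.** The protocol states no safety event rate, margin or power, so there is no safety figure to reproduce. As an illustration, take n = 80 per arm (section 17) and assume that 8 patients in an arm have drug-related AEs, none of them due to the pump. Exact (Clopper-Pearson) 95% limits are:

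- Drug-related: 8/80 = 10.0%, limits 4.4% to 18.8%.
- Pump-related: 0/80 = 0%, upper limit 1 − 0.025^(1/80) = 4.5%.

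The 10% is an assumption. The discrepancy has the same form at any non-zero rate.

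**5. Does the all-AE comparison replace the related-AE comparison?** Only in part. With the same assumed excess of 8 patients in one active arm against placebo (two-sided Fisher's exact test):

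- Related AEs, 8/80 against 0/80: p = 0.007.
- Any AE on an assumed 30% background, 32/80 against 24/80: p = 0.25.
- Any AE on an assumed 50% background, 48/80 against 40/80: p = 0.27.

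The any-AE rows assume that the 8 patients would otherwise have had no AE. An excess concentrated in one event type could still show in the by-type tables. A scattered one might not.

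**6. Sample size.** The figure of 240 rests on the WHO-scale ANOVA (f = 0.20, α = 0.05) and uses no safety quantity, so correcting the safety wording does not affect it.

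**The case against.** The strongest reply is that *device* is leftover template wording for study product. The only causality field available is the one in section 14.2, so an analyst would most plausibly use it and no harm would follow. That is probably how the text arose, and the pump reading is the less likely one. It does not make the variable correct as written: the replacement must still be inferred, and section 17 gives no threshold for relatedness.

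A reader might go further and infer that the planned analysis misses drug-related harm, or that the favourable-safety claim would rest on a variable that cannot show harm. The documents do not support that:

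- The same Fisher sentence compares all SAEs, and all AEs by type and overall, regardless of attribution. In a randomised comparison this does not depend on anyone's causality judgement.
- Section 17 also has each SAE listed and discussed individually.
- A gastrointestinal excess would appear in the by-type comparison. A liver-enzyme effect could appear there and in the biochemistry panel, which includes ALT, AST, ALP and bilirubin.
- Drug-related AEs remain a named secondary outcome.
- The formal success rule in section 17 concerns only the change in the WHO scale. No decision rule uses the device variable.

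Nor can the variable both lack source data and read zero. Taken literally it is underivable. The 0/80 figure arises only if *device* is taken to mean the pump.

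It might also be argued that the definite-or-probable limit in section 9.2 is itself a fault because it leaves out possibly related events. Nothing in the protocol contradicts that limit, and widening it is a matter of preference.

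**Conclusion.** The point holds in this form. The primary safety variable and every relatedness-based comparison in section 17 are defined on a device that the trial does not define. They are inconsistent with sections 14.2, 14.3 and 9.2, and cannot be derived from the causality data as collected. Read as pump-related, they would leave out drug-related events: 0/80 in place of 8/80 in the illustration, which rests on an assumed 10% rate.

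The damage is confined to the headline safety variable and the related-event tables. Data collection is intact, comparisons that do not depend on attribution are planned, and neither the efficacy success rule nor the sample size is touched. It is a definition error in a named primary variable. It is simple to correct and should be corrected before unblinding.

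**What to change.** In section 17, under Safety Endpoints and Safety Analysis:

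1. Replace the device-related wording with relation to study product, and name the section 14.2 causality assessment as the source. The primary safety variable then becomes the cumulative incidence, with 95% CI, of AEs related to study product. The related-SAE and related-AE comparisons follow the same definition.
2. State which causality categories count as related, consistently with the definite-or-probable outcome in section 9.2. A wider summary that includes possible may be added, but is not required.
3. Delete the adverse device reaction and device malfunction rates, or define them explicitly for the spray pump and say how they will be recorded.
4. Keep the comparisons of all SAEs and all AEs as they stand.

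The cost is a wording amendment. The first two changes need no new data, and neither does the third if those rates are deleted. Keeping pump malfunctions would require somewhere to record them. The sample size does not change.
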